 6. Time course of the response in eyes treated with GS010 IVT injection compared to eyes treated with sham IVT injection, for the BCVA reported with LogMAR, for parameters measured with HVF 30-2 and for parameters measured with SD-OCT, with comparisons from the RESCUE or REVERSE study baselines and pooled, to each follow-up study time point (2, 2.5, 3, 4, and 5 years) using mixed effects models with repeated measures (MMRM).
 7. Time course of the response in eyes treated with GS010 IVT injection compared to eyes treated with sham IVT injection, for contrast sensitivity measured with the Pelli-Robson chart with comparisons from the RESCUE or REVERSE study baselines and pooled, to follow-up study time points (2, 3, 4, and 5 years) using MMRM.
 8. Visual improvement as measured by LogMAR by analysis of covariance (ANCOVA) to determine the difference in improvement for all-GS010 eyes compared to all-sham eyes, for best-GS010 eyes compared to best-sham eyes and for worst-GS010 eyes compared to worst-sham eyes, with comparisons from the RESCUE or REVERSE study baselines and pooled, to each follow-up study time point (2, 2.5, 3, 4, and 5 years).
 9. Change of ganglion cell layer (GCL) thickness/volume and topographical map and other parameters measured by SD-OCT (e.g., retinal nerve fiber layer and quadrantal thickness analyses) for all-GS010 eyes compared to all-sham eyes, for best-GS010 eyes compared to best-sham eyes and for worst-GS010 eyes compared to worst-sham eyes, from the RESCUE or REVERSE study baselines and pooled, to each follow-up study time point (2, 2.5, 3, 4, and 5 years) using (MMRM).

10. QOL as measured with the Visual Functioning Questionnaire 25 (VFQ-25) and 36-Item Short Form Health Survey, version 2 (SF-36-v2) subject-rated instruments and summarized descriptively with within-group comparisons from the RESCUE or REVERSE study baselines and pooled, to each follow-up study time point (2, 2.5, 3, 4, and 5 years).

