11.5.2.5 Time Course Analysis

Time course analysis will compare time course of the response up to Visit 5 (Year 5) using MMRM (Mixed Model Repeated Measure) procedure. The change from baseline in the LogMAR and change from baseline in log of contrast sensitivity (LogCS) will be the responses. The change from baseline of all-GS010 eyes will be compared to the change from baseline of all-sham eyes using a MMRM including the subject and the eyes of the subject as random factors, the treatment, follow-up visit, eye status at baseline (better or worse), interaction between baseline values and treatment, interaction between linear time from onset of disease and treatment, interaction between eye status at baseline and treatment, interaction between linear time and treatment and baseline LogMAR as predictors in the model. The estimate of treatment effect at various follow-up time points and its 95% confidence interval (CI) (without adjustment for multiplicity) will be presented. Compound symmetry structure will be fitted. In case of any convergence problem with this covariance structure, other covariance structures will be used.

Time course analysis of Humphrey visual field parameters and SD-OCT parameters will be conducted similarly to the time course analysis of LogMAR (details will be provided in the SAP).

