8. STATISTICAL METHODS

All analyses will be performed on SAS Version 9.4 or higher.

Unless otherwise noted, categorical and binary variables will be summarized using counts and percentages. Percentages will be rounded to one decimal place.

Continuous variables will be summarized using the number of observations (n), mean, standard deviation (SD), median, first quartile (Q1), third quartile (Q3), minimum and maximum. Change from baseline or from nadir will also be summarized by a 95% confidence interval (CI).

Least square means, 95% CIs, and p-values will be reported from ANCOVA models. Estimated proportions with 95% CIs will be provided for Generalized Estimating Equation (GEE) models and for logistic regression models for responder endpoints. ANCOVA models will be run on all continuous endpoints, logistic regression for all subject responder endpoints, and GEE models for all eye responder endpoints.

Rounding rules are generally as follows:

- If the original variable has x decimal places, then minimum and maximum will be reported with x decimal places; mean, median, Q1, Q3, SD and CIs will be reported with x+1 decimal places.
- P-values will be reported with four decimal places.

Summary TFLs will display standard headers containing the sponsor name (“GenSight Biologics”) as well as a standard footer containing the name of the program used to generate the display, its path, and a date stamp. Headers, footers, titles, and column headers for tables will be repeated on every page of each display; pages will be numbered “Page x of y.” Visit labels in tables and figures will show visit name. Summary TFLs containing no applicable data will display a line reading, “No applicable data were reported” or similar wording. Dates and times will be presented using SAS DATE9. and SAS TIME5. formats.

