- The change of LogMAR BCVA from nadir to the visit of interest

Analysis for European Medicines Agency (EMA)

The primary analysis will be performed on the mITT Population. The change from baseline to each follow-up visit in the LogMAR acuity will be the response. The change from baseline of all-GS010 eyes will be compared to the change from baseline of all-sham eyes applying a mixed-effects ANCOVA model using the following terms (or covariate) in the model:

- Subject as a random factor.
- The baseline LogMAR as a covariate.
- Treatment as a fixed effect.

The null and alternative hypotheses for the EMA LogMAR analysis are:

$$H_0: \mu_{\text{All-GS010}} = \mu_{\text{All-Sham}}$$

$$H_1: \mu_{\text{All-GS010}} \neq \mu_{\text{All-Sham}},$$

where μ presents the mean change from baseline to the visit of interest in LogMAR and “All” represents all eyes treated with GS010 or Sham.

The investigative site will not be included in the analysis as the number of subjects recruited per site will be very small. However, stratification by geographical area may be performed as a sensitivity analysis. Neighboring countries can be pooled to reach at least 9 subjects per geographical entity. The analysis will be performed using an alpha of 0.05 (two-sided test).

An additional model may add the treatment by geographical interaction (geographical areas: USA and Europe) to investigate the generalizability of the treatment effect. The following model diagnostics may be checked: normality of error terms, independence of error terms, independence of the covariate and treatment effect, and homogeneity of error variances.

Analysis for Food and Drug Administration

The primary analysis will be based on the mITT Population. The change from baseline of the best-GS010 treated eyes will be compared to the change from baseline of the best-sham eyes (inter-subject comparison) using an ANCOVA with baseline LogMAR as covariate. The analysis will be performed using an alpha of 0.05 (two-sided test). The statistical significance in favor of the best-GS010 treated eyes against the best-sham eyes will show evidence of the advantage of using GS010 for halting visual acuity loss or improving visual acuity in subjects with LHON. The difference in the mean change from baseline (adjusted mean difference) between the two treatment groups and associated 95% confidence interval will be reported.

The null and alternative hypotheses for the FDA LogMAR analysis are:

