8.7 EXPLORATORY ANALYSES

8.7.1 Exploratory efficacy analyses

As an exploratory analysis, the response to treatment through Visit 5 (Year 5) using a MMRM model will be performed. The change from baseline in the LogMAR will be the response. Change from baseline of all-GS010 eyes will be compared to the change from baseline of all-sham eyes. The model will include subject as a random factor and fixed effects for treatment, follow-up visit (time point), eye status at baseline (better or worse), time from onset of disease and LogMAR at baseline as a covariate. The following interactions will be explored: baseline LogMAR and treatment; time from onset of disease and treatment; and eye status at baseline and treatment. The estimate of treatment effect at various follow-up time points and its 95% confidence interval (CI) will be presented. A UN@AR(1) (Autoregressive(1)) covariance structure will be fit to accommodate the doubly repeated measures data (repeated over time and eye). In the event of convergence problems with this covariance structure, other covariance structures will be explored.

Time course analysis of log of contrast sensitivity (LogCS), Humphrey visual field parameters and SD-OCT parameters will be conducted similarly to the time course analysis of LogMAR.

Other exploratory analyses will be performed for all analysed visits as a sensitivity analysis, excluding off-chart evaluations whose distance to the subject was superior to 2 meters. The endpoints analysed will be the ones described in 8.5.2.2 at eye level.

Additional exploratory analyses may be performed in the study.

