8.8 CHANGES FROM ANALYSES PLANNED IN THE PROTOCOL

The following changes from the analyses planned in the protocol were made in the SAP based on previous experience from RESCUE and REVERSE studies. These updates are not in contradiction with the protocol; as some analyses are considered not valuable or necessary for the current study, they are therefore removed from the plan.

- The additional statistical models for the LogMAR primary analysis for the EMA and FDA, that were planned to add the treatment by geographical interaction for lack of generalizability of treatment effect, will not be performed. The main-effect test will still be performed.

-
- As per the protocol, QoL assessments should have been collected at Visit 2 (Year 2.5). However, because it was decided it was not required, these data were therefore not collected and will not be summarized.
 - Change of ganglion cell layer (GCL) thickness and topographical map will not be a part of the analyses as these data will not be assessed as initially planned in the protocol.
 - The Pediatric Population and subset populations are included in addition to the populations included in the protocol. Selected outputs are also planned to be produced based on these populations.
 - For doubly repeated measures MMRM models, the protocol specified that: “Compound symmetry structure will be fitted. In case of any convergence problem with this covariance structure, other covariance structures will be used.” Following further statistical considerations, UN@AR(1) (Unstructured @ Autoregressive(1)) covariance structure will be used instead. In case of any convergence problem with this covariance structure, other covariance structures will be explored.
 - According to the protocol, the subject and the eyes of the subject were considered random effect in the statistical model. The analyses will not include the eyes of the subjects as a random effect.
 - GEE models will be used instead of McNemar tests. Logistic regression will be used in place of Fisher’s exact tests. The new models will provide the opportunity to control for baseline.
 - Time-course analyses are designated exploratory, as the building of the model with multiple effects and interactions is an exploratory exercise.
 - A Per Protocol analysis population has been added for efficacy analyses.
 - Graphical representations and regressions of OCT parameters were added

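### The time-course MMRM in SAP 8.7.1 has no treatment-by-visit term, so as listed it gives one GS010-sham difference for all visits; the protocol's time-by-treatment term was dropped without an entry in SAP 8.8

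*SAP*

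**What the plan says.** SAP 8.7.1 models change from baseline in LogMAR over all follow-up visits. The fixed effects are treatment, visit, eye status at baseline, time from disease onset and baseline LogMAR; subject is random, and the covariance is UN@AR(1). On interactions it says: "The following interactions will be explored: baseline LogMAR and treatment; time from onset of disease and treatment; and eye status at baseline and treatment". On output it says: "The estimate of treatment effect at various follow-up time points and its 95% confidence interval (CI) will be presented". The same approach is then applied to LogCS, Humphrey visual field and SD-OCT parameters.

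Protocol 11.5.2.5 specifies the same kind of model with four treatment interactions. The first is with the baseline value. The others are listed as "interaction between linear time from onset of disease and treatment, interaction between eye status at baseline and treatment, interaction between linear time and treatment".

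SAP 8.8 lists several changes to this model. On covariance: "Following further statistical considerations, UN@AR(1) (Unstructured @ Autoregressive(1)) covariance structure will be used instead". On status: "Time-course analyses are designated exploratory, as the building of the model with multiple effects and interactions is an exploratory exercise". It also records that eye is no longer a random effect. It does not mention the linear time-by-treatment interaction.

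Outside the MMRM, SAP 8.5.2.2 plans an ANCOVA visit by visit for LogMAR ("The change from baseline to each follow-up visit in the LogMAR acuity will be the response"), and SAP 8 says more generally that "ANCOVA models will be run on all continuous endpoints".

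**The concern.** A model with treatment and visit only as main effects assumes that the GS010-sham difference is the same at every visit. That conflicts with the output promised in the same paragraph, and it departs from the protocol without a record.

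The assumption also removes the question a time-course model is there to answer. Protocol 5.3 gives the regulatory reason for longer observation: to learn whether efficacy lasts, declines, or takes more time to appear. Each of these is a treatment-by-time question. The protocol named MMRM as the method for its time-course secondary endpoints 6 and 7 (endpoint 6 begins "Time course of the response in eyes treated with GS010 IVT injection compared to eyes treated with sham IVT injection, for the BCVA"). It is the only planned GS010-sham model fitted across visits. The per-visit ANCOVAs and responder models take one visit at a time, so they give no interval or test for a change in the effect between visits.

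A programmer working from the list would produce a pooled average labelled Year 5. It would stand beside a Year 5 ANCOVA estimate that may disagree with it, and the same would happen for LogCS, visual field and SD-OCT.

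**Working it through.** **1. Which terms can move the contrast.** The documents give no figure to reproduce here, so the check is on the model itself. The contrast at visit v is L(v) = x(GS010, v) − x(sham, v), where x is the row of fixed-effect covariates.

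| Treatment interaction | Protocol 11.5.2.5 | SAP 8.7.1 | Varies by visit? |
|---|---|---|---|
| Baseline value | yes | yes | no |
| Time from onset | yes | yes | no, if fixed at baseline |
| Eye status at baseline | yes | yes | no |
| Linear time | yes | **absent** | yes |

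The visit main effect cancels in L(v). What remains is treatment plus interactions with baseline quantities, so L(v) is the same for all v. The random effect and UN@AR(1) do not enter L(v). The text says the three interactions are to be explored, but no subset of them changes this result.

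**2. Is time from onset fixed?** SAP 8.7.1 does not say. SAP 4.4 refers to duration of vision loss at the time of treatment, SAP 5.4 derives vision-loss duration from onset to the baseline date, and the protocol lists onset time and linear time as two separate interactions. A baseline quantity is the consistent reading.

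**3. Simulation of the listed model.** Assumed inputs: 60 subjects, two eyes, five visits, random subject intercept, and a true effect widening from −0.05 to −0.28 LogMAR.

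| Model | Year 2 | 2.5 | 3 | 4 | 5 |
|---|---|---|---|---|---|
| True effect | −0.05 | −0.08 | −0.12 | −0.20 | −0.28 |
| SAP as listed | −0.195 | −0.195 | −0.195 | −0.195 | −0.195 |
| With protocol's linear time × treatment | −0.090 | −0.130 | −0.171 | −0.251 | −0.332 |
| With categorical visit × treatment | −0.099 | −0.106 | −0.182 | −0.263 | −0.325 |

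The listed model gave SE 0.0125 at every visit. If onset time were updated at each visit, its interaction with treatment would act as a linear trend (−0.081 at Year 2 to −0.342 at Year 5).

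**4. What the single estimate averages.** Each subject has one GS010 eye and one sham eye, so take the between-eye difference at each visit, with correlation matrix V, equal variances and complete data. AR(1) is taken by visit order. The common-effect estimate weights the visits by w = V⁻¹1 / (1′V⁻¹1). Under AR(1) with correlation ρ and five visits, w is proportional to (1, 1−ρ, 1−ρ, 1−ρ, 1), so the Year 5 weight is 1 / (2 + 3(1−ρ)):

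- ρ = 0.6: 1/3.2 = 0.313
- ρ = 0.8: 1/2.6 = 0.385
- ρ = 0.9: 1/2.3 = 0.435
- compound symmetry, any correlation: 1/5 = 0.20

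For LogCS (Years 2, 3, 4, 5) the Year 5 weight is 1 / (2 + 2(1−ρ)) = 0.357, 0.417 and 0.455, or 0.25 under compound symmetry.

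**5. Size of the error at Year 5** (five visits, effect as a fraction of its full size). Waning is (1, 1, 1, 0.5, 0). Emerging is (0, 1/6, 1/3, 2/3, 1).

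| Correlation | Waning, SAP model (truth 0) | Waning, linear term (truth 0) | Emerging, SAP model (truth 1) |
|---|---|---|---|
| AR(1) 0.6 | 0.625 | 0.025 | 0.458 |
| AR(1) 0.8 | 0.577 | −0.024 | 0.474 |
| AR(1) 0.9 | 0.543 | −0.058 | 0.486 |
| Compound symmetry | 0.700 | 0.099 | 0.433 |

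Example, ρ = 0.6, waning: 0.3125 + 0.125 + 0.125 + 0.125 × 0.5 + 0 = 0.625. In the emerging case the linear term recovers 1.0. As a check, 400 simulated two-eye trials under waning with UN@AR(1) at ρ = 0.8 gave a mean of 0.576 at every visit for the listed model. With treatment-by-visit they gave 1.00, 1.00, 1.00, 0.50, 0.00.

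**6. Precision cost of freeing the visits.** The ratio of per-visit to pooled SE is √(1′V⁻¹1). For AR(1) with five visits this is √((5 − 3ρ)/(1 + ρ)) = 1.41, 1.20, 1.10 at ρ = 0.6, 0.8, 0.9. For compound symmetry it is √(5/(1 + 4ρ)) = 1.21, 1.09, 1.04. For LogCS the ratios are 1.32, 1.15, 1.08 and 1.20, 1.08, 1.04.

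**The case against.** The strongest reply is that the paragraph states its own output. A programmer asked for effects by time point would need a term that yields them, the interaction list is not declared closed, and SAP 8.8 calls the model-building exploratory. This may well be a drafting slip. That lessens the blame but not the need to correct it: the written list and the written output cannot both be followed.

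A second reply is that time from onset might be updated at each visit, which would let the effect change linearly. SAP 8.7.1 does not exclude this, so the identical-estimates result is conditional on the baseline reading. SAP 4.4 and 5.4 and the protocol's separate terms make the alternative unlikely, and it too would need to be written down.

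Third, the impact is limited. The MMRM is exploratory and its demotion is recorded. All efficacy is secondary, and per-visit ANCOVAs, responder comparisons and plotted curves still show a change over time. This stands, and it is why no primary conclusion is at risk. What those displays lack is an interval or test for the change.

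Fourth, the protocol promised neither a joint test nor categorical visit. That is true; restoring linear time-by-treatment would remove the formal contradiction. It would still force a straight line on estimates presented visit by visit.

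Finally, the widest figures come from compound symmetry, which the SAP replaced. Under AR(1) alone the ranges are 31% to 43% for the Year 5 weight, 54% to 63% for waning and 46% to 49% for emerging.

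**Conclusion.** The concern holds and should be fixed. With time from onset fixed at baseline, the model in SAP 8.7.1 returns one GS010-sham difference for every visit, contradicts the output it promises, and omits a protocol term with no entry in 8.8.

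The size depends on the true time course. A constant effect gives no bias. Under the assumed correlations, 57% to 80% of the weight in the LogMAR figure labelled Year 5 comes from earlier visits (55% to 75% for LogCS). In the illustrative waning case the model shows 54% to 70% of the early effect where none remains. In the emerging case it shows 43% to 49% of the true effect. These percentages do not depend on sample size or SD. They rest on the assumed correlations and effect patterns, equal variances and complete data.

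**What to change.** In SAP 8.7.1, make treatment-by-visit, with visit as a factor, a mandatory fixed effect for LogMAR, LogCS, visual field and SD-OCT. Report the per-visit GS010-sham contrasts with 95% intervals and the joint treatment-by-visit test from that model. Keep the three baseline-factor interactions as exploratory additions, and state that time from onset is measured at baseline. Record in SAP 8.8 that the categorical term replaces the protocol's linear time-by-treatment term.

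The cost is one model term, one joint test, a clarifying phrase and one line in 8.8; no new data are needed. Per-visit intervals would be about 4% to 41% wider than the pooled interval (4% to 32% for LogCS). That is the price of letting the effect differ by visit.

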8.7.2 Exploratory safety analyses

In order to perform following analyses, a medical review will be done to review all ocular AEs and classify them as Intraocular inflammation AE / Elevation of IOP AE (including the following terms: IOP increase, intraocular hypertension).

Additional medical review will be performed to identify concomitant treatments categories:

- Local IOP lowering agent,
- Systemic IOP lowering agent,
- Combination local and systemic lowering agents
- Local (topical) Corticosteroid (CS),
- Systemic CS.
- Combination local (topical) and systemic CS

The following descriptions will be made for GS010 eyes, SHAM eyes and overall.

8.7.2.1 Treatment for AEs related to elevation of IOP

Treatment of AEs with elevation of IOP will be described with number of eyes and events using treatment (None/IOP agent lowering local alone/IOP agent lowering systemic alone/ local and systemic in association) during the long-term follow-up visits (2, 2.5, 3, 4, and 5 years).

Duration of treatment will be described.

8.7.2.2 Treatment for AEs related to intraocular inflammation

Treatment of AEs related to an intraocular inflammation will be described with number of eyes and events using corticoids (None/local CS alone/systemic CS alone/ local and systemic in association) during the long-term follow-up visits (2, 2.5, 3, 4, and 5 years). Number and percent of inflamed eyes will be described for each type of CS (local CS alone/systemic CS alone/ local and systemic in association) during the long-term follow-up visits (2, 2.5, 3, 4, and 5 years).

Duration of treatment under CS will be described.

8.8 CHANGES FROM ANALYSES PLANNED IN THE PROTOCOL

The following changes from the analyses planned in the protocol were made in the SAP based on previous experience from RESCUE and REVERSE studies. These updates are not in contradiction with the protocol; as some analyses are considered not valuable or necessary for the current study, they are therefore removed from the plan.

- The additional statistical models for the LogMAR primary analysis for the EMA and FDA, that were planned to add the treatment by geographical interaction for lack of generalizability of treatment effect, will not be performed. The main-effect test will still be performed.

-
- As per the protocol, QoL assessments should have been collected at Visit 2 (Year 2.5). However, because it was decided it was not required, these data were therefore not collected and will not be summarized.
 - Change of ganglion cell layer (GCL) thickness and topographical map will not be a part of the analyses as these data will not be assessed as initially planned in the protocol.
 - The Pediatric Population and subset populations are included in addition to the populations included in the protocol. Selected outputs are also planned to be produced based on these populations.
 - For doubly repeated measures MMRM models, the protocol specified that: “Compound symmetry structure will be fitted. In case of any convergence problem with this covariance structure, other covariance structures will be used.” Following further statistical considerations, UN@AR(1) (Unstructured @ Autoregressive(1)) covariance structure will be used instead. In case of any convergence problem with this covariance structure, other covariance structures will be explored.
 - According to the protocol, the subject and the eyes of the subject were considered random effect in the statistical model. The analyses will not include the eyes of the subjects as a random effect.
 - GEE models will be used instead of McNemar tests. Logistic regression will be used in place of Fisher’s exact tests. The new models will provide the opportunity to control for baseline.
 - Time-course analyses are designated exploratory, as the building of the model with multiple effects and interactions is an exploratory exercise.
 - A Per Protocol analysis population has been added for efficacy analyses.
 - Graphical representations and regressions of OCT parameters were added
 - Exploratory safety analyses were added to describe treatments of eyes with intraocular inflammation and elevation of IOP.

